#### **2.1.6 Placebo-to-benralizumab extension analysis set**

All participants who received benralizumab at the start of the extension period who were previously randomised to placebo treatment.

### **2.2 Violations and deviations**

Participants who do not meet eligibility criteria but are still randomised and received at least 1 dose of IP will be analysed according to the analysis sets described in Section 2.1. There is no intention to perform a per-protocol analysis in this study.

#### **2.2.1 Important protocol deviations**

Important protocol deviations are a subset of protocol deviations that may significantly impact the completeness, accuracy, and/or reliability of the study data or that may significantly affect a participant's rights, safety, or well-being.

The final list of important protocol deviations will be documented prior to unblinding the study data (primary DBL) and will include but may not be limited to the following categories:

- Eligibility criteria not met (participants incorrectly randomised)
  - Deviations from key inclusion criteria
  - Deviations from key exclusion criteria
- Deviations from informed consent procedures
- Discontinuation criteria for IP met but participant not withdrawn from study treatment
- Deviations from IP management and administration
- Received prohibited/restricted concomitant medication
- Other important protocol deviations
  - Scheduled study assessments not done or incorrectly performed at baseline and/or >3 post-baseline visits in the same year (separately for UPDD assessments, physical examination, vital signs, safety lab tests, pregnancy tests)

- Unblinding of treatment assignment for reasons unrelated to participant safety
- Other severe non-compliance (such deviations will be clearly described in the CSR)

Only important protocol deviations will be summarised and listed in the CSR.

### **2.2.2 Impact on analyses due to COVID-19 pandemic**

Given the uncertainty surrounding the future impact of the COVID-19 worldwide pandemic on clinical trials, operational procedures are being implemented in this study to maintain the integrity of collected data. Efforts may be made to collect data via alternative means where possible, when on-site visits cannot be performed.

If there is a sufficient number of protocol deviations or study disruptions as a result of COVID-19, then sensitivity analyses may be conducted to evaluate their impact on the interpretation of results. Protocol deviations, including doses or visits missed due to COVID-19 related protocol deviations will be described separately in the CSR. Confirmed or suspected cases of COVID-19 will be listed and included as AEs as appropriate.

## **3 PRIMARY AND SECONDARY VARIABLES**

### **3.1 General definitions**

#### **3.1.1 Baseline definition**

Generally for efficacy data, the last recorded value on or prior to the date of randomisation will serve as the baseline measurement. If time is collected, the assessment performed the same day but at a time prior to randomisation will be included in the baseline definition.

Generally for safety data, the last recorded value on or prior to the first dose of study treatment will serve as the baseline measurement. If time is collected, the assessment performed the same day but at a time prior to the first dose of study treatment will be included in the baseline definition.

For PROs calculated from daily scores, assessments prior to the date of randomisation will be used for baseline. The weekly scores will be calculated using the 7 days prior to the day of randomisation as baseline. If there is no value prior to the date of randomisation, then the baseline value will not be imputed and will be set to missing. Further details on scoring for daily PROs will be provided in Sections [3.2](#) and [3.3](#).

For PROs with recall periods of 1 week or more, the time component of the definition of baseline (i.e. time of assessment relative to randomisation) will not be considered; assessments on the same day as randomisation will be used for baseline. If there is no value prior to randomisation (or the same day), then the baseline value will not be imputed and will be set to missing. Further details on scoring for PROs will be provided in Sections [3.3](#) and [3.5](#).

When time of assessment is not recorded or missing, it is assumed that assessments recorded on the date of first dose of study treatment were performed prior to dosing, except in cases of protocol specified post-dose assessments. If there is no value prior to randomisation (or the first dose of study treatment, depending on the endpoint), then the baseline value will not be imputed and will be set to missing. No data known to be collected post first dose will be used in determining the baseline value, unless otherwise specified.

For laboratory results and vital signs, baseline will be defined as the last non-missing assessment prior to first dose of study treatment will be used as baseline. If no time is recorded for an assessment, and the assessment takes place at Visit 2, this will be assumed to be a pre-dose assessment. For physical examinations (complete or brief) baseline data will be collected at Visit 2 before first dose of IP.

Additional analyses for the participants who switch from placebo to benralizumab at Week 24 may be performed where the baseline value is set to the last recorded value prior to starting benralizumab (i.e. likely the Week 24 measurement) to obtain an assessment of the changes occurring while actually receiving benralizumab.

### **3.1.2 Change from baseline**

Absolute change from baseline outcome variables are computed as

$(\text{post-baseline value} - \text{baseline value})$ .

Percent change from baseline outcome variables are computed as:

$((\text{post-baseline value} - \text{baseline value}) / (\text{baseline value})) * 100$

If either the post-baseline value or the baseline value is missing, then both change from baseline and percent change from baseline value will also be set to missing. If the baseline value is zero, the percent change will be set to missing.

### **3.1.3 Visit windows**

For PROs calculated from daily scores, scheduled visit days will be used. The weekly scores will be calculated using the 7 days prior to the day of the scheduled visit assessment. Thus, the primary and key secondary endpoint assessments will be based on the actual 7 days before the Week 12 scheduled visit. No visit window will be applied to the scheduled visit day. Further details on scoring for daily PROs will be provided in Sections 3.2 and 3.3.

For efficacy endpoints that present visit-based data, visit windows will be applied. The adjusted analysis-defined windows will be based on the collection schedule listed in the protocol and variables will be windowed to the closest scheduled visit for that variable.

Visit windows following baseline will be constructed in such a way that the upper limit of the interval falls half way between two visits (the lower limit of the first post-baseline visit will be study day 2). If an even number of days exists between two consecutive visits, then the upper limit will be taken as the midpoint value minus 1 day. Visit windows are constructed so that every observation collected can be allocated to a particular visit. No visit windows will be defined for screening visits.

For assignment of data to adjusted analysis-defined visit windows, study day will be defined as follows:

$$(Date \text{ of } assessment - date \text{ of } randomisation) + 1$$

By this definition, the day of randomisation will be study day 1 and the planned date of Visit 3 (Week 4) will be study day 29 (=28+1), for example.

If multiple assessments are recorded within a single adjusted visit window, please refer to the rules below.

- If there are 2 or more observations within the same visit window, then the non-missing observation closest to the scheduled study day will be used in the analysis.
- If 2 observations are equidistant from the scheduled study day, then the non-missing observation with the earlier collection date will be used in the analysis.
- If 2 observations are collected on the same day then the non-missing observation with the earlier collection time will be included in the analysis.

If a visit window does not contain any observations, then the data will remain missing.

For endpoints which are not collected at every visit (including PROs with recall periods of 1 week or more), the above rules will be applied to derive adjusted analysis-defined visit windows based on the protocol defined visit schedule for that endpoint.

Similarly, visit windows will be applied for laboratory parameters. Vital signs will be based on the case report form (CRF) visit designation.

When IP dosing needs to be postponed, it is recommended that all scheduled treatment visit procedures (except for IP administration) are still performed within the visit window. For further details see CSP Section 6.1.2.

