Weekly PRO: PGI-S	At site at Visits 1 and 2. At home every 7 ± 3 days after Visit 2.
Monthly PROs: UCT, DLQI, CU-Q ₂₀ L	At site at Visits 1 and 2. At home every 28 ± 3 days after Visit 2.
EQ-5D-5L	At site at Visits 1, 2, 3, 4, 5, and 15.
CCI	[REDACTED]

^a Morning is defined as 05:00 to 12:00 on day *n*.

^b Evening is defined as 17:00 on Day *n* to 04:00 on Day *n* + 1.

CU-Q₂₀L, Chronic Urticaria Quality of Life Questionnaire; DLQI, Dermatology Life Quality Index; EQ-5D-5L, European Quality of Life-5 Dimensions; CCI [REDACTED] PGI-S, Patient Global Impression of Severity; PRO, patient-reported outcomes; UCT, Urticaria Control Test; UPDD, Urticaria Patient Daily Diary.

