4.1.2 Investigational Product Dosing Regimen

Participants who meet entry criteria will be randomised 3:3:3:3:4 by the interactive voice/web response system (Interactive Voice Response System [IVRS]/Interactive Web Response System [IWRs]) to one of the 5 treatment sequences described in Section [4.1](#).

[Figure 3](#) presents an overview of the IP that will be administered for each randomised treatment group.

Figure 3 Investigational Product Administration

^a In the extension period, participants will receive benralizumab on a Q8W or Q4W dosing regimen, as predetermined at randomisation (Visit 2). Participants randomised to receive benralizumab Q8W in the extension period will also receive placebo at intervening study visits when they are not receiving benralizumab.

Q4W, every 4 weeks; Q8W, every 8 weeks.

Dosing Regimen at Visits 2, 3, and 4 (Initial Double-blind 12-week Treatment Period)

All participants will receive randomised double-blind study medication Q4W at Visits 2, 3 and 4 (ie, Weeks 0, 4, and 8; [Figure 3](#)).

Dosing Regimen at Visits 5, 6, and 7

Participants randomised to receive either 60 mg or 30 mg benralizumab during the initial 12-week period will receive 30 mg benralizumab Q4W at Visits 5, 6 and 7 (ie, Weeks 12, 16 and 20; [Figure 3](#)).

Participants receiving placebo will continue to receive placebo ([Figure 3](#)).

Dosing Regimen at Visits 8 Through 14

At Week 24 (Visit 8), participants initially randomised to benralizumab 60 mg or benralizumab 30 mg will receive benralizumab 30 mg Q4W or Q8W according to their original randomisation at Week 2. Participants randomised to the Q8W regimen will receive placebo at Week 24 and benralizumab 30 mg at Week 28 ([Figure 3](#)).

At Weeks 24, 28, and 32 (ie, Visits 8, 9 and 10), participants initially randomised to placebo will receive benralizumab 30 mg Q4W. At Week 36 (ie, Visit 11), participants randomised initially to placebo will receive benralizumab 30 mg Q8W; these participants will receive placebo at Week 36 and benralizumab 30 mg at Week 40 (Visit 12) ([Figure 3](#)).

Participants transitioned to the benralizumab 30 mg Q8W dosing regimen will remain on the Q8W dosing regimen. Participants will continue to receive SC injections Q4W at the study site visits; thus, participants receiving benralizumab 30 mg Q8W will receive placebo at every other site visit ([Figure 3](#)).

The final dose of benralizumab or placebo will be administered at Week 48 (Visit 14).

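### SAP 3.1.3 does not close the double-blind analysis windows at the first extension dose, so a late Week 24 questionnaire or off-schedule laboratory sample taken on benralizumab can be labelled as placebo data

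*SAP*

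**What the plan says.** SAP 3.1.3 counts the day of randomisation as study day 1 and gives one worked figure: "the planned date of Visit 3 (Week 4) will be study day 29". Windows are built so that "the upper limit of the interval falls half way between two visits", and when the number of days between visits is even, "the upper limit will be taken as the midpoint value minus 1 day". The section adds that "Visit windows are constructed so that every observation collected can be allocated to a particular visit". If a window holds several values, "then the non-missing observation closest to the scheduled study day will be used in the analysis", and ties go to the earlier value.

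These windows apply to visit-based efficacy endpoints, to questionnaires with a recall of a week or more, and to laboratory parameters, each on its own collection schedule. Daily-diary scores are not windowed and use the seven days before the visit. Vital signs keep the visit label from the case report form.

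Protocol 4.1.2 dates the switch: "At Weeks 24, 28, and 32 (ie, Visits 8, 9 and 10), participants initially randomised to placebo will receive benralizumab 30 mg Q4W". For UCT, DLQI and CU-Q2oL, Protocol 1.3 (Table 3) sets the post-randomisation schedule as "At home every 28 ± 3 days after Visit 2".

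Two other SAP sections treat the switch as a boundary. SAP 3.4.1 ends the double-blind adverse event period on the day before the first extension dose. SAP 3.1.1, on re-baselining placebo participants, expects their last value before benralizumab usually to be the Week 24 one.

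**The concern.** The placebo arm receives its first active dose at Visit 8, close to the middle of the Week 24 window for the monthly questionnaires. The windowing rule looks only at distance from the planned study day and not at whether the dose has been given. A questionnaire completed after that dose but inside the window would be analysed as placebo Week 24 data.

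Change from baseline in UCT, DLQI and CU-Q2oL at Week 24 are secondary endpoints analysed by MMRM against placebo. Only the placebo arm (n = 40) goes from placebo to active drug at this point, so any mislabelling is one-sided. If benralizumab works, it would pull the Week 24 difference towards zero. For laboratory data, a sample taken on benralizumab could appear in the placebo column of the 24-week safety summaries.

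Because the SAP already cuts adverse events at this dose, the absence of a cut for windowed data reads as an omission rather than a choice.

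**Working it through.** **Inputs**
- Study day of Week w = 7w + 1 (SAP 3.1.3).
- Upper window limit = midpoint of two consecutive scheduled days, minus 1 day if the gap is even (SAP 3.1.3). For an odd gap the midpoint is rounded down, which is my reading.
- First benralizumab dose in the placebo arm: Week 24, Visit 8 (Protocol 4.1.2).
- Site visits from Visit 3 on have a tolerance of ± 3 days (Protocol 1.3, Table 2).
- Monthly questionnaires every 28 ± 3 days and PGI-S every 7 ± 3 days, both after Visit 2 (Protocol 1.3, Table 3).

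**Check of the SAP's own figure.** Week 4: 7 × 4 + 1 = 29, which matches.

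**Planned switch.** Week 24: 7 × 24 + 1 = Day 169. With the tolerance, Visit 8 falls on Days 166 to 172.

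**UCT, DLQI, CU-Q2oL (28-day schedule)**
- Lower limit: Week 20 is Day 141. (141 + 169)/2 = 155, minus 1 = 154, so the Week 24 window opens on Day 155.
- Upper limit: Week 28 is Day 197. (169 + 197)/2 = 183, minus 1 = Day 182.
- Overrun: 182 − 169 = 13 days. With Visit 8 on Day 172 or Day 166 it is 10 or 16 days.
- If the days between are counted as the 27 intervening days (odd), the limit is Day 183 and the overrun 14 days.

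**PGI-S (weekly schedule).** Week 25 is Day 176. (169 + 176)/2 = 172.5, rounded down to Day 172. Overrun: 172 − 169 = 3 days.

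**Laboratory values.** The result depends on which visits are laboratory visits:

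| Laboratory visits assumed | Days | Upper limit | Days past Day 169 |
|---|---|---|---|
| Weeks 20 and 40 (Table 2 as printed) | 141, 281 | 211 − 1 = 210 | 41 |
| Weeks 24 and 44 (if columns shifted) | 169, 309 | 239 − 1 = 238 | 69 |
| Weeks 24 and 52 (if columns shifted) | 169, 365 | 267 − 1 = 266 | 97 |

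On the printed schedule the window that contains the switch is Week 20, and there is no Week 24 laboratory window. The other two rows are assumptions about a table that may have been damaged by extraction.

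**What can actually enter.** The Week 24 monthly questionnaire is due on Days 166 to 172. The next is due on Days 194 to 200, outside the window. So only a Week 24 questionnaire completed late, with no pre-dose value nearer Day 169, can bring post-dose data into the window.

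**How much of the recall would be post-dose.** As an illustration, take a dose on Day 169 and a questionnaire on the last window day, 13 days later. UCT recalls 4 weeks (13/28 = 46%), CU-Q2oL 2 weeks (13/14 = 93%) and DLQI 1 week (all 7 days). These are ceilings for one very late questionnaire, not expected values.

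**The case against.** The strongest reply is that conduct rules already close most of the route. The text above Table 3 in Protocol 1.3 requires questionnaires that are within their window and still open at a site visit to be completed there before anything else. Protocol 8.1 also puts available assessments ahead of other procedures, and Protocol 6.1.1 says samples and on-site questionnaires should precede dosing.

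A reader might pair a visit on Day 166 with a questionnaire on Day 172 and infer that the rules allow a 6-day lag after the dose. They do not. The questionnaires run from Visit 2, and Protocol 6.1.2 calculates visits from randomisation, so both windows are Days 166 to 172. On any permitted Visit 8 date the questionnaire is already within its window and must come before the dose. A 6-day lag needs a protocol deviation.

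A reader might also apply the 13 days to laboratory values or call them Week 24 data. SAP 3.1.3 windows each variable on its own schedule, so neither follows.

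Nor is Week 24 efficacy broadly contaminated. ISS7, UAS7, HSS7, the UAS7 responder endpoints and the angioedema measures count back seven days from the visit and exclude the visit day. The three exposed secondary endpoints lie outside the multiplicity procedure in SAP 4.1.1.

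All of this stands, and it narrows the point. It does not remove it. The protocol rules govern conduct and do not say how a late value is analysed, and SAP 3.1.3 would accept it. For laboratory data, Protocol 8 lets assessments be postponed when kits are missing, and SAP 3.4 uses unscheduled and repeat values. The nearest-day rule can even favour a post-dose sample. If Week 24 were a laboratory visit, a repeat on Day 170 (1 day from Day 169) would displace a pre-dose sample from Day 166 (3 days away).

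**Conclusion.** The gap is real but small. SAP 3.1.3 lets double-blind windows run past the first extension dose: by 13 days for UCT, DLQI and CU-Q2oL, by about 3 days for PGI-S, and by more than 13 days for laboratory values (41 as printed, subject to the state of that table). These figures are the length of window left open, not the exposure of a typical participant.

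With the protocol followed, exposure is limited to late or missed questionnaires and to postponed, repeat or unscheduled laboratory samples. A reader might infer a material bias in the Week 24 comparison. The documents give no rate of late assessments and no early effect size, so neither the number affected nor the shift can be computed. The direction, towards no difference, holds only if benralizumab works.

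The diary-based endpoints, vital signs and Week 12 results are unaffected. This assumes that diary scores count back from the visit as attended. The point is a cheap improvement, not a threat to the trial's main conclusions.

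**What to change.** Add to SAP 3.1.3: in all arms, for participants who enter the extension, only observations on or before the first extension dose (pre-dose where a time is recorded) are eligible for double-blind visit windows. Later observations go to the next scheduled visit for that variable.

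The cut should be dated by the first extension injection, active or placebo, because Protocol 4.1.2 gives the Q8W arms placebo at Week 24. Using the actual date also covers a postponed Week 24 dose. Applying it in all arms keeps the groups on the same rule and in line with the adverse event cut in SAP 3.4.1.

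**Cost.** One sentence. A few Week 24 values become missing or are relabelled, including some from benralizumab participants who had no placebo-to-active switch. Relabelled questionnaires will rarely be used at Week 28: a Day 175 value is 197 − 175 = 22 days from target, against at most 3 days for one completed on schedule. A relabelled laboratory sample can lie far from its new visit (on the printed schedule, Day 175 to Week 40 is 281 − 175 = 106 days), but it is used only if no closer sample exists.

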### **3.1.4 Prior/concomitant medications**

Medications will be categorized according to the WHO Drug Reference List dictionary which employs the Anatomical Therapeutic Chemical (ATC) classification system.

A medication will be regarded as prior if it was stopped on or before the date of randomisation (medication stop date  $\leq$  date of randomisation).

A medication will be regarded as ‘concomitant’ if the start date is on or after the date of randomisation or if it started prior to the date of randomisation and was ongoing after the date of randomisation. If a medication was started and stopped on the date of randomisation, it will be considered as concomitant.

No medication data will be imputed. The handling of partial/missing dates for AEs and prior/concomitant medications is detailed in [Appendix 8.3](#). Duration of AEs and prior/concomitant medications will not be calculated using imputed dates and will instead be set to missing.

Throughout the study, participants will be required to maintain stable doses of their pre-randomisation H1 antihistamine treatment (CSP Section 6.5.1). Participants will be permitted to use additional doses (up to 4 x recommended dose per day) of the pre-randomization H1 antihistamine on days on which symptoms become intolerable, and use should be documented in the ePRO device. A switch of the rescue medication for an individual participant is not permitted (CSP Section 6.5.3).

The number of tablets of rescue medication taken is recorded in the handheld ePRO device as part of the daily Urticaria Patient Daily Diary (UPDD):

- During the past 24 hours, how many tablets of rescue medication did you use in order to control symptoms of your skin condition such as itch or hives?

The weekly number of days of taking rescue medication is calculated by summing the daily use of rescue medication (taken) over the past 7 days. The weekly average amount of anti-histamine medication (including background and rescue) is calculated by summing the recorded multiple of licensed dose taken each day over the past 7 days, and dividing by 7 days. Participants who took no rescue medication and only their daily background medication as per protocol would be presented as 1 time the licensed dose of anti-histamine medication.

For each visit, the 7 daily responses prior to that visit will be used for calculating the weekly scores, thus the day of the visit will not be included into the weekly score. These derivations will be consistent to the definition of the primary endpoint variable.

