**Table 2 Assessment of CSU itch activity in study participants**

Score	Itch severity
0	None
1	Mild
2	Moderate
3	Severe

Scoring criteria are as defined in omalizumab Study Q4882g (EUDRACT: 2010-022785-27).

The mean of the morning and evening itch scores for each day is taken as the ISS for the day. For daily ISS, if either the morning or evening score is missing, the non-missing score for that day (morning or evening) is used as the daily score. If both morning and evening scores are missing, the daily score is not calculated. The ISS7 is the sum of ISS for the previous 7 days.

If a participant has at least 4 non-missing ISS scores, the ISS7 is defined as the sum of the available daily ISS scores divided by the number of days with non-missing ISS scores, multiplied by 7. If there are less than 4 non-missing daily ISS scores then the weekly ISS7 is missing for that week.

For each visit, the 7 daily scores prior to that visit will be used for calculating the weekly scores, thus the day of the visit will not be included into the weekly score.

The minimum ISS7 is 0 and the maximum is 21. The baseline ISS7 will be the sum of the ISS during the 7 days prior to day of randomisation. The ISS7 at Week 12 will be the sum of the daily ISS during the previous 7 days.

For the primary estimand, all available scheduled visit data up to Week 24 will be included regardless of intercurrent events like randomised treatment adherence, rescue medication received, or early discontinuation. The primary analysis will follow a treatment policy approach with missing at random assumption.

Participants will complete all PRO assessments using a handheld device. The handheld device will be the only accepted source of PRO data. In case of technical issues with the device, a web-based emulator of the device will be available.

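### As written, SAP 3.1.4 divides weekly antihistamine use by a fixed 7 days and has no rule for unanswered diary days, so incomplete weeks read low in the descriptive rescue summaries

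*SAP*

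**What the plan says.** SAP 3.1.4 derives two weekly variables from the daily diary.

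- Rescue days: "The weekly number of days of taking rescue medication is calculated by summing the daily use of rescue medication (taken) over the past 7 days".
- Average antihistamine amount, background and rescue together: "calculated by summing the recorded multiple of licensed dose taken each day over the past 7 days, and dividing by 7 days".

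The section gives its own reference value: a participant who takes only background medication "would be presented as 1 time the licensed dose of anti-histamine medication". On missing entries it says "No medication data will be imputed" and nothing more. It ends by fixing which seven days before a visit are used, followed by "These derivations will be consistent to the definition of the primary endpoint variable".

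SAP 3.2 treats gaps in the itch score from the same diary explicitly. Within a day, "if either the morning or evening score is missing, the non-missing score for that day (morning or evening) is used as the daily score". Within a week with at least 4 scored days, ISS7 is "the sum of the available daily ISS scores divided by the number of days with non-missing ISS scores, multiplied by 7". Below that, "If there are less than 4 non-missing daily ISS scores then the weekly ISS7 is missing for that week". SAP 3.3.6 also divides angioedema-free days by the number of days answered.

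**The concern.** If the formula is programmed as it stands, a day with no entry adds nothing to the numerator but stays in the divisor. The participant then appears to have taken no antihistamine that day, not even the background dose. The rescue-day count has the same weakness, because an unanswered day is indistinguishable from a day without rescue.

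These variables matter for interpretation. The primary estimand follows a treatment-policy strategy, so itch scores are kept whatever rescue was taken, and rescue may reach four times the labelled dose (Protocol 6.5.3). Descriptive summaries by group are how a reader judges whether antihistamine use was similar across groups. SAP 4.2.7.1 also makes the optional sensitivity analyses for UAS7 depend partly on how much rescue was used. SAP 8.1 itself names incomplete diary use as a source of missing data, so incomplete weeks are foreseen.

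**Working it through.** **Inputs.** The fixed divisor of 7, the plain sum of rescue days, the absence of imputation and the 1-time reference value come from SAP 3.1.4. The ISS7 rule comes from SAP 3.2. The number of recorded days, k, is an assumption, because the documents give no diary-completion rate. I use k = 4 to 6, the incomplete weeks that would still meet a 4-day minimum, and add k = 3 for contrast.

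**Step 1: reproduce the plan's figure.** Weekly average = (sum of recorded daily multiples) / 7. Seven recorded days at 1× give 7/7 = 1.00, which matches the SAP. The match needs all seven days.

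**Step 2: apply the formula literally to incomplete weeks.** For steady use at multiple m, the result is m × k/7 and the shortfall is 1 − k/7.

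| Recorded days k | Shortfall | True 1× reads | True 2× reads | True 4× reads |
|---|---|---|---|---|
| 7 | 0% | 1.00 | 2.00 | 4.00 |
| 6 | 14.3% | 0.86 | 1.71 | 3.43 |
| 5 | 28.6% | 0.71 | 1.43 | 2.86 |
| 4 | 42.9% | 0.57 | 1.14 | 2.29 |
| 3 | 57.1% | 0.43 | 0.86 | 1.71 |

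The shortfall is in total antihistamine use, so part of it is background dose and not rescue.

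**Step 3: rescue days.** A participant who records rescue on each of 4 answered days gets 4 under the plain sum. Scaled to answered days, the value is 4/4 × 7 = 7.

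**Step 4: compare with ISS7.** With 4 scored days at a daily score of 2, the raw sum is 8 and ISS7 is 8/4 × 7 = 14. The itch score is restored to a full week, while the antihistamine average from 4 recorded days is not. With 3 scored days ISS7 is missing, whereas the fixed divisor still returns a value from 3 recorded days.

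**Step 5: result with the divisor changed.** (m × k)/k = m for any k of 4 or more, so background-only use reads 1.00 at 4, 5 or 6 days. Below 4 days the value is missing.

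**Step 6: does the closing sentence supply the rule?** Two other places in the SAP bear on this.

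- SAP 3.3.6 uses near-identical wording about consistency with the primary endpoint, directly after saying which seven days count, and yet states its own denominator. There the wording concerns the choice of days.
- SAP 3.3.1 does import the ISS7 rule for HSS7 and UAS7, and names missing data when it does so. SAP 3.1.4 does not.

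The more natural reading is that the sentence fixes the seven-day window only. The importing reading remains possible. On the two readings, programmers could report 0.57× and 1.00× for the same 4-day background-only week.

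**The case against.** The strongest reply is that the SAP never says an unanswered day scores zero. Scoring it so could be called imputation, which the section rules out, and it would break the section's own reference value. The closing sentence may carry the ISS7 rule across. Dividing by 7 may be shorthand for a complete week, since SAP 3.2 also first describes ISS7 as a seven-day sum and gives the missing-day rule afterwards. This stands to the extent that zero-scoring is a consequence of the literal formula and not a stated intention. It does not remove the gap, because SAP 3.2 goes on to state its rule and SAP 3.1.4 does not.

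A reader might infer several stronger things that the documents do not support.

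- **That the section contradicts its consistency statement.** If that sentence is about the seven-day window, there is no contradiction. If it covers missing days, the ISS7 rule already applies.
- **That the shortfall falls exactly where ISS7 is corrected.** A day is lost to ISS7 only when both the morning and the evening score are missing. Rescue is a single 24-hour item and can be missing on a day that keeps its itch score. Below 4 days ISS7 is set to missing, not corrected.
- **That comparisons between arms will be distorted.** This needs diary completion to differ by arm. If completion averaged 6.5 and 5.5 days (pure assumption) at a true 2×, the readings would be 2 × 6.5/7 = 1.86 and 2 × 5.5/7 = 1.57, a false gap of 0.29×. Nothing in the documents points to such a difference. Protocol 5.1 sets run-in diary thresholds, Protocol 8.1 requires compliance checks at least weekly, and SAP 8.1.1 tabulates missing daily ISS7 and UAS7 assessments by group and visit, though not the rescue item.
- **That efficacy results are affected.** They are not. SAP 4.2.3 does not name the weekly average among its summaries, and SAP 4.2.6.3 defines substantial rescue use on daily dosing.

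**Conclusion.** The point holds as a defect in a written derivation with limited reach. Taken literally, the formula understates steady antihistamine use by 14% to 43% for weeks with 6 down to 4 recorded days, and it no longer returns the value that the section gives for background-only use. The percentages are exact for a given k under steady use. How often such weeks would occur is unknown.

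The consequence is confined to descriptive antihistamine and rescue summaries. These inform how the treatment-policy result is read and may influence whether optional rescue sensitivity analyses are run. The primary MMRM and the daily-use definition of substantial rescue are unaffected. The documents do not establish that missing days will always be counted as zero, because the closing sentence of SAP 3.1.4 leaves room for the ISS7 rule. The correction is still worth making, since it costs almost nothing and removes the ambiguity.

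**What to change.** In SAP 3.1.4:

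1. Divide the summed multiples of licensed dose by the number of days in the window with a non-missing rescue response, not by 7.
2. Require at least 4 such days, as for ISS7; otherwise set the weekly value to missing.
3. Report weekly rescue days as (rescue days / non-missing days) × 7 under the same 4-day rule.

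The cost is a wording change and the reprogramming of these weekly derivations, with no new data. The downside is that participant-weeks with fewer than 4 answered days become missing where they would otherwise have shown a falsely low value. These should be few if diary compliance is kept up, but the documents give no rate from which to count them.
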